CT	Chlamydia trachomatis
CRF	Case Report Form
DCF	Data Collection Form
DMID	Division of Microbiology and Infectious Diseases
DSMB	Data and Safety Monitoring Board
eCRF	Electronic Case Report Form
FDA	Food and Drug Administration
GC	N. gonorrhoeae
GI	Gastrointestinal
HIV	Human Immunodeficiency Virus
HMC	Harborview Medical Center
ICF	Informed Consent Form
ICH	International Conference on Harmonisation
IDES	Internet Data Entry System
IDS	Investigational Drug Services
IRB	Institutional Review Board
ITT	Intention-To-Treat
LGV	Lymphogranuloma Venereum
MOP	Manual of Procedures
MSM	Men who have Sex with Men
N	Number (typically refers to subjects)
NAAT	Nucleic Acid Amplification Test
NIH	National Institutes of Health
OTC	Over-the-Counter
PCR	Polymerase Chain Reaction
PI	Principal Investigator
PP	Per Protocol

List of Abbreviations (continued)

PrEP	Pre-exposure prophylaxis
SAE	Serious Adverse Event
SAP	Statistical Analysis Plan
STD	Sexually Transmitted Disease
STI	Sexually Transmitted Infection
US	United States
UW	University of Washington
WHO	World Health Organization

1. PREFACE

The Statistical Analysis Plan (SAP) for “A Phase 4, Randomized, Double-Blinded, Placebo-Controlled Trial of Azithromycin versus Doxycycline for the Treatment of Rectal Chlamydia in Men who have Sex with Men” (DMID Protocol 17-0092) describes and expands upon the statistical information presented in the protocol.

This document describes all planned analyses and provides reasons and justifications for these analyses. It also includes sample tables, listings, and figures planned for the interim analyses and final analyses. Regarding the interim analyses, the final analyses and manuscript, this SAP follows the International Conference on Harmonisation (ICH) of Technical Requirements for Registration of Pharmaceuticals for Human Use Guidelines and is consistent with Topic E8 (General Considerations for Clinical Trials) and Topic E9 (Statistical Principles for Clinical Trials). The structure and content of the SAP provides sufficient detail to meet the requirements identified by the Food and Drug Administration (FDA) and ICH, while all work planned and reported for this SAP will follow internationally accepted guidelines published by the American Statistical Association and the Royal Statistical Society for statistical practice.

This document contains four sections: (1) a review of the study design, (2) general statistical considerations, (3) comprehensive statistical analysis methods for efficacy and safety outcomes, and (4) a list of proposed tables, listings and figures. Any deviation from this SAP will be described and justified in protocol amendments and/or the manuscript, as appropriate. The reader of this SAP is encouraged to also review the study protocol for details on conduct of the study and the operational aspects of clinical assessments.

2. INTRODUCTION

2.1. Study Background

Chlamydia is the most frequently reported bacterial sexually transmitted infection (STI) in the US. In 2015, approximately 1.5 million cases of chlamydia were reported to Centers for Disease Control and Prevention (CDC) from 50 states and the District of Columbia, but an estimated 2.9 million infections occur annually. Rectal *Chlamydia trachomatis* (CT) infection is the most common bacterial STI among MSM in the US [reference 1 in the protocol], the population at highest risk for HIV infection. Therefore, effective treatment of rectal CT is a key component of chlamydia control, and perhaps HIV prevention, for MSM. Studies in diverse healthcare settings have found that 8-12% of asymptomatic MSM test positive for rectal CT [references 2-5 in the protocol].

The 2015 CDC Sexually Transmitted Disease (STD) Treatment Guidelines for CT infection of any anatomic site recommend either a single dose of azithromycin or a 7-day course of twice-daily doxycycline. However, in practice, many clinicians treat asymptomatic rectal CT with azithromycin rather than doxycycline due to the relative simplicity of a single-dose regimen, although this varies geographically across the US [reference 6 in the protocol]. The CDC's treatment recommendation is extrapolated from studies of azithromycin and doxycycline for the treatment of urogenital CT, but doxycycline may be more effective than azithromycin for the treatment of rectal CT. A well designed and conducted trial comparing the efficacy of the two recommended treatments could inform CDC's STD Treatment Guidelines for chlamydia in MSM and clinical practice.

There are several possible explanations why doxycycline could be superior to azithromycin in the treatment of rectal CT. First, older randomized studies of azithromycin vs. doxycycline were limited to genital CT infections, while rectal CT may differ from genital CT infections due to host-microbial interactions. A study of chlamydial infection in mice found that doses of azithromycin that cured genital infections were ineffectual in eradicating gastrointestinal (GI) infections. This occurred despite comparable levels of azithromycin in both anatomic tracts. In contrast, doxycycline had similar efficacy in curing GI and genital tract infections [reference 7 in the protocol]. Second, some strains of CT may have evolved to be less susceptible to azithromycin. Although azithromycin resistance among CT has never been conclusively demonstrated, evolution of antimicrobial resistance remains a possibility. Third, LGV, due to infection with L-serovar strains of CT, differentially causes proctitis, and some studies suggest that LGV is under-detected[reference 8 in the protocol]. Treatment with a single dose of azithromycin may be less effective than a 7-day regimen of doxycycline in the treatment of undetected LGV. Although these factors could explain the consistent findings in observational studies that doxycycline is superior to azithromycin, residual confounding remains a possible explanation. To date, only non-randomized retrospective studies have compared the effectiveness of doxycycline and azithromycin for the treatment of rectal CT[reference 9 in the protocol]. Two potential explanations for the observed differences in observational studies include differential clinician prescription of azithromycin and doxycycline and different sexual behavior in patients who receive a single dose of medication vs. a 7-day course of medication. A placebo-blinded, randomized controlled trial is necessary to definitively compare the clinical efficacy of azithromycin vs. doxycycline for the treatment of rectal CT.

We hypothesize that doxycycline will be more effective than azithromycin in achieving microbiologic cure of rectal CT. To test this, we will screen and enroll MSM diagnosed with rectal CT into a randomized, double-blinded, placebo-controlled trial of azithromycin vs. doxycycline. The primary study outcome will be microbiologic cure (negative rectal CT NAAT result) 28 days after initiation of treatment.

2.2. Purpose of the Analyses

These analyses will assess the efficacy and safety of azithromycin 1-gram single dose or doxycycline 100 mg twice daily for 7 days for the treatment of rectal CT in MSM and will be included in the final manuscript.

3. STUDY OBJECTIVES AND ENDPOINTS

3.1. Study Objectives

3.1.1. Primary Objective

To compare the efficacy of azithromycin vs. doxycycline for treatment of rectal CT infection in MSM based on microbiologic cure (negative NAAT) at Day 29.

3.1.2. Secondary Objectives

- 1 To assess the effect of LGV infection on microbiologic cure in MSM with rectal CT at Days 15 and 29.
- 2 To compare the efficacy of azithromycin vs. doxycycline for treatment of rectal CT in MSM based on microbiologic cure at Day 15.

3.1.3. Exploratory Objective

To assess the effect of HIV status, adherence to study drug, antacid medication use and symptomatic status on microbiologic cure at Day 29.

3.2. Endpoints

3.2.1. Primary Outcome Measure

The proportion of subjects with microbiologic cure in each study arm at Day 29.

3.2.2. Secondary Outcome Measures

- 1 The proportion of subjects with microbiologic cure in each study arm at Days 15 and 29 within subgroups defined by LGV infection at baseline.
- 2 The proportion of subjects with microbiologic cure in each study arm at Day 15.

3.2.3. Exploratory Outcome Measures

The proportion of subjects with microbiologic cure in each study arm at Day 29 within separate subgroups defined by HIV status at baseline, adherence to study drug, antacid medication use and symptomatic status.

3.3. Study Definitions and Derived Variables

3.3.1. Microbiologic Cure Status at Visit 3

Microbiologic cure will be based on rectal CT NAAT results. For the primary analysis, microbiologic cure at Visit 3 (Day 29) will be defined using the criteria in [Table 1](#) below.

Table 1: Interpretation of Rectal CT NAAT Results for Day 29 Analyses

Visit 2 (Day 15) NAAT Result	Visit 3 (Day 29) NAAT Result	Clinical Interpretation at Visit 3 (Day 29)	Microbiologic Cure Status for Primary Analysis
Negative	Negative	Cure	Cure
Negative	Positive	Reinfection or Recrudescence	Failure
Negative	Unknown	Unknown	Unknown
Positive	Negative	Delayed RNA clearance	Cure
Positive	Positive	Failure	Failure
Positive	Unknown	Unknown	Unknown
Unknown	Negative	Cure or Delayed RNA clearance	Cure
Unknown	Positive	Reinfection or Recrudescence	Failure
Unknown	Unknown	Unknown	Unknown

Subjects will be classified as non-evaluable if they:

- did not return for Visit 3, or
- their NAAT results at Visit 3 were not available for any reason, or
- they could not be evaluated for microbiological outcome status at Visit 3 for any other reason.

3.3.2. Microbiologic Cure Status at Visit 2

Microbiologic cure status at Visit 2 (Day 15) will be defined using the criteria in [Table 2](#) below.

Table 2: Interpretation of Rectal CT NAAT Results for Day 15 Analyses

Visit 2 (Day 15) NAAT Result	Clinical Interpretation at Visit 2 (Day 15)	Microbiologic Cure Status for Secondary Analysis
Negative	Cure	Cure
Positive	Failure	Failure
Unknown	Unknown	Unknown

Subjects will be classified as non-evaluable if they:

- did not return for Visit 2, or
- their NAAT results at Visit 2 were not available for any reason, or
- they could not be evaluated for microbiological outcome status at Visit 2 for any other reason.

3.3.3. Within Window Test of Cure Visit

Test of Cure Visit 2 will be considered within window if the visit occurred between Days 12 and 18 (inclusive) after the first dose of study drug.

Test of Cure Visit 3 will be considered within window if the visit occurred between Days 25 and 31 (inclusive) after the first dose of study drug.

3.3.4. Treatment Adherence

Subjects will be considered sufficiently adherent with study treatment if they take the initial dose of azithromycin (or placebo) and initial dose of doxycycline (or placebo) and at least 9 additional doses of doxycycline (or placebo) within 10 days (inclusive) of the completed initial dose.

An alternative definition of sufficiently adherent will also be explored. Subjects will be considered sufficiently adherent under this alternate definition if they:

- take the initial dose of azithromycin (or placebo) and initial dose of doxycycline (or placebo), and
- take at least 80% of the scheduled doses of doxycycline capsule (or placebo) (i.e., at least 12 of the 14 doses) as assessed by the subject-reported number of missed doses within in 7 days (inclusive) of the completed initial dose.

3.3.5. Initial Completed Dose and Timing of Subsequent Doses

Subjects will be considered to have taken the initial dose of azithromycin (or placebo) and initial dose of doxycycline (or placebo) in the clinic if they are observed to take the doses and do not report vomiting within two hours of administration.

If a subject vomits, he is able to return to the study clinic for retreatment within 48 hours. If he returns within 48 hours and is able to swallow the doses and not vomit within two hours of administration, he will be considered to have taken the initial dose of azithromycin (or placebo) and initial dose of doxycycline (or placebo).

For subjects who take the initial dose and do not report vomiting, the timing requirements for sufficiently adherent determination described in Section 3.3.4 (i.e. within 10/7 days of completed initial dose) will be with respect to the initial study clinic visit date. For subjects who take the retreatment dose, the timing requirements will be with respect to the retreatment visit date for azithromycin (or placebo) and for the earliest completed dose of doxycycline (or placebo) as applicable (e.g., at the retreatment visit or in the interim following the vomited dose, prior to the retreatment visit).

3.3.6. Baseline Value

The baseline value will be defined as the last value obtained prior to the first dose of study products.

3.3.7. LGV Infection Status

The LGV infections status is determined by the laboratory multiplex polymerase chain reaction (PCR) test. If LGV strains of CT are detected at baseline, the subject's LGV infection status will be classified as positive. Otherwise, the subject will be classified as negative.

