3.2.2 Secondary Outcome Measures

- The proportion of subjects with microbiologic cure in each study arm at Days 15 and 29 within subgroups defined by LGV infection at baseline
- The proportion of subjects with microbiologic cure in each study arm at Day 15

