6.1.1. Pseudo Code

The following SAS® pseudo code will be used to calculate the following:

Chi-Square test at 5% two-sided significance level and odds ratio (and 95% asymptotic CI):

```
proc freq;
  Table treatment*analysis_variable / chisq;
  ods output ChiSq=outputdsn1;
  ods output RelativeRisks=outputdsn2;
run;
```

Fisher's Exact test at 5% two-sided significance level:

```
proc freq;
  Table treatment*analysis_variable / exact;
  ods output FishersExact=outputdsn;
run;
```

95% Wilson CI for proportions/percentages:

```
proc freq;
  Table treatment*analysisvariable / binomial(wilson);
  ods output binomialcls=outputdsn;
run;
```

95% Wilson CI for difference in proportions (produces Newcombe CI):

```
proc freq;
  Table treatment*analysisvariable / riskdiff(cl=Wilson);
  Exact Riskdiff;
  ods output pdiffcls=outputdsn;
run;
```

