6.5. Missing Data

Subjects with unknown microbiologic cure status will be excluded from the CC and PP population. For ITT analyses, such subjects will be included with their cure status imputed as microbiological failures.

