8.2.2. Secondary Efficacy Analyses

The first secondary efficacy endpoint is the proportion of subjects with microbiologic cure in each study arm at Day 15. The number of subjects, the proportion of subjects with microbiologic cure at Visit 2 (Day 15) will be summarized overall and by treatment. The same analyses as described in the previous section will be performed for the Visit 2 (Day 15) outcome (excluding O'Brien Fleming bound comparisons). See [Table 16](#), [Table 17](#), and [Table 18](#).

The second secondary efficacy endpoint is the proportion of subjects with microbiologic cure in each treatment arm at Days 15 and 29 within subgroups defined by LGV infection at baseline. The number of subjects, the proportion of subjects with microbiologic cure at Visit 2 (Day 15) and Visit 3 (Day 29) will be summarized in each subgroup overall and by treatment. The point estimates for treatment-specific proportions and difference in proportions as well as corresponding 95% Wilson confidence intervals will be present within each subgroup at Visit 2 (Day 15) and Visit 3 (Day 29) for each analysis population. See [Table 19](#), [Table 20](#), [Table 21](#), [Table 22](#), [Table 23](#), and [Table 24](#).

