Table 14: Microbiologic Cure at Visit 3 (Day 29) by Treatment Group - ITT Population**Table 15: Microbiologic Cure at Visit 3 (Day 29) by Treatment Group - PP Population****Table 16: Microbiologic Cure at Visit 2 (Day 15) by Treatment Group - CC Population****Table 17: Microbiologic Cure at Visit 2 (Day 15) by Treatment Group - ITT Population****Table 18: Microbiologic Cure at Visit 2 (Day 15) by Treatment Group - PP Population**

Implementation Notes:

Test Statistic and Critical Value columns are not applicable for Table 14 to Table 18 and thus will be excluded.

Table 19: Microbiologic Cure at Visit 3 (Day 29) by Treatment Group and Baseline LGV Infection Status - CC Population

Treatment Group	Number of Subjects with Microbiologic Cure n	Number of Subjects N	Proportion of Subjects with Microbiologic Cure	Proportion of Subjects with Microbiologic Cure 95% CI	Difference in Proportion of Subjects with Microbiologic Cure between Doxycycline and Azithromycin	Difference in Proportion of Subjects with Microbiologic Cure between Doxycycline and Azithromycin 95% CI
LGV Negative						
Doxycycline	x	x	0.xx	0.xx, 0.xx	0.xx	0.xx, 0.xx
Azithromycin	x	x	0.xx	0.xx, 0.xx		
All Subjects	x	x	0.xx	0.xx, 0.xx		
LGV Positive						
Doxycycline	x	x	0.xx	0.xx, 0.xx	0.xx	0.xx, 0.xx
Azithromycin	x	x	0.xx	0.xx, 0.xx		
All Subjects	x	x	0.xx	0.xx, 0.xx		

Note: The denominator for proportions is based on the number of subjects enrolled in the respective treatment group.

Tables with similar format:

Table 20: Microbiologic Cure at Visit 3 (Day 29) by Treatment Group and Baseline LGV Infection Status - ITT Population

Table 21: Microbiologic Cure at Visit 3 (Day 29) by Treatment Group and Baseline LGV Infection Status - PP Population

Table 22: Microbiologic Cure at Visit 2 (Day 15) by Treatment Group and Baseline LGV Infection Status - CC Population

Table 23: Microbiologic Cure at Visit 2 (Day 15) by Treatment Group and Baseline LGV Infection Status - ITT Population

Table 24: Microbiologic Cure at Visit 2 (Day 15) by Treatment Group and Baseline LGV Infection Status - PP Population

Table 25: Microbiologic Cure at Visit 3 (Day 29) by Treatment Group and Baseline HIV Status - CC Population

Table 26: Microbiologic Cure at Visit 3 (Day 29) by Treatment Group and Baseline HIV Status - ITT Population

Table 27: Microbiologic Cure at Visit 3 (Day 29) by Treatment Group and Baseline HIV Status - PP Population

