Site	Deviation Description	Start Day	End Day	Reason for Deviation	Deviation Resulted in Subject Termination?	Deviation Affected Product Stability?	Deviation met immediate IRB reporting requirement?	Deviation Category	Deviation Resolution	Comments
xxxx	xxxx	xx	xx	xxxx	Yes/No	Yes/No/NA	Yes/No	xxxx	xxxx	xxxx
xxxx	xxxx	xx	xx	xxxx	Yes/No	Yes/No/NA	Yes/No	xxxx	xxxx	xxxx

Implementation Notes:

1. Sort order will be by Site, Start Day.
2. In the Deviation Description column concatenate any specify fields.
3. In the Reason for Deviation column concatenate any specify fields.

Listing 6: Individual Efficacy Response Data- All Enrolled Subjects

Actual Treatment Group	Randomized Treatment Group	Subject ID	Baseline LGV Infection Status	Baseline HIV Status	Visit 2 (Day 15) Rectal CT NAAT Result	Visit 3 (Day 29) Rectal CT NAAT Result
Azithromycin/ Doxycycline	Azithromycin/ Doxycycline	xxxxxx	Non-LGV/LGV/Indeterminate/Not Done	Negative/ Positive/Unknown	Negative/Positive/ Indeterminate/Not Done	Negative/Positive/ Indeterminate/Not Done
Azithromycin/ Doxycycline	Azithromycin/ Doxycycline	xxxxxx	Non-LGV/LGV/Indeterminate/Not Done	Negative/ Positive/Unknown	Negative/Positive/ Indeterminate/Not Done	Negative/Positive/ Indeterminate/Not Done

Implementation Notes:

1. Sort order will be by Actual Treatment Group, Subject ID, Baseline LGV Infection Status.
2. If all subjects received the correct treatment, only display a single “Treatment Group” column.

Listing 7: Demographic and Baseline Characteristics - All Enrolled Subjects

Actual Treatment Group	Randomized Treatment Group	Subject ID	Age at Enrollment (years)	Ethnicity	Race	Symptomatic Status	Inguinal Lymphadenopathy
Azithromycin/Doxycycline	Azithromycin/Doxycycline	xxxxxx	xx	xxxxxx	xxxxxx	Symptomatic/ Asymptomatic	Yes/No
Azithromycin/Doxycycline	Azithromycin/Doxycycline	xxxxxx	xx	xxxxxx	xxxxxx	Symptomatic/ Asymptomatic	Yes/No

Implementation Notes:

1. Sort order will be by Actual Treatment Group, Subject ID.
2. For the Race column, if a subject is Multi-Racial, all races will be listed, separated by a comma.
3. If subject was a screen failure, populate Actual Treatment Group and Randomized Treatment Group with “—“.
4. If all subjects received the correct treatment, only display a single “Treatment Group” column.

Listing 8: STD History - All Enrolled Subjects

Timepoint	Diagnosed STDs ^a (Start Date / End Date)	Self-Reported HIV Status ^b (Date of Testing or Diagnosis)	On Antiretroviral Therapy? ^c

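### SAP 3.3.7 counts untyped men as LGV-negative, and Tables 19-24 give no interval for the effect of LGV on cure (minor; secondary analysis only)

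*SAP*

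**What the plan says.** SAP 3.3.7 defines LGV status from the multiplex PCR. Detection at baseline makes a man positive; for every other result, "Otherwise, the subject will be classified as negative". The Listing 6 shell records the baseline result as "Non-LGV/LGV/Indeterminate/Not Done". Protocol 8.2.2 runs the PCR only on CT-positive specimens. SAP 6.3.2.1 keeps every randomized man in ITT, whatever his baseline NAAT result.

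The missing-data rule in SAP 6.5 concerns the outcome only: "Subjects with unknown microbiologic cure status will be excluded from the CC and PP population", with imputation as failure in ITT.

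The first objective in SAP 3.1.2 is "To assess the effect of LGV infection on microbiologic cure in MSM with rectal CT at Days 15 and 29". The matching outcome measure (Protocol 3.2.2, repeated in SAP 3.2.2) is cure by arm "within subgroups defined by LGV infection at baseline". SAP 8.2.2 plans: "The point estimates for treatment-specific proportions and difference in proportions as well as corresponding 95% Wilson confidence intervals will be present within each subgroup". In the Table 19 shell, which Tables 20-24 share, the one contrast is "Difference in Proportion of Subjects with Microbiologic Cure between Doxycycline and Azithromycin". SAP 12 plans no further analyses.

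**The concern.** **Classification.** A man whose PCR failed or was not run has unknown LGV status, yet the rule reports him as LGV-negative. The stratum then mixes men typed as non-LGV with men not typed, and no summary table says how many. Listing 6 shows them one by one. The SAP treats NAAT outcomes differently: its own Tables 1 and 2 keep Unknown as a category.

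**Contrast.** The objective asks how LGV affects cure. The tables answer whether the drugs differ within each LGV stratum. A reader can subtract the LGV-negative row from the LGV-positive row, but no interval is given for the result. With few LGV cases, a bare 20-point gap could be over-read.

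**Working it through.** The documents state no figure for the LGV analysis, so there is none to reproduce. From SAP Section 5 come 246 evaluable men (123 per arm) and the 97%/87% row of Table 3. LGV prevalence, untyped rate and cure in LGV cases are assumptions. A single central laboratory (SAP 6.7) and the acute-proctitis exclusion (Protocol 5.2) point to the low ends of the ranges.

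**1. Untyped men in the LGV-negative stratum, CC population**

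Let *L* be the LGV prevalence (5, 10, 15%) and *m* the untyped share, unrelated to strain (1 to 20%).

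- Untyped men per arm: 123*m* = 1.2 to 24.6.
- True LGV share of the stratum labelled negative: *s* = *Lm* / [(1 - *L*) + *Lm*]. Lowest: 0.0005/0.9505 = 0.05%. Highest: 0.03/0.88 = 3.4%.
- Azithromycin cure in that stratum: 0.87(1 - *s*) + *cs*, with LGV cure *c* = 40% or 60%. Range 85.40% to 86.99%, against 87%. With *m* at most 5%, the lowest value is 86.59%.
- Doxycycline cure: 0.97(1 - *s*) + *ds*, with *d* = 90% or 97%. The treatment difference reads 10.01 to 11.60 points instead of 10.00. With *m* at most 5%, the highest is 10.41.

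**2. ITT, with CT-negative baseline swabs**

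Assume 8% LGV, 85% cure in typed non-LGV men and 98% Day 29 negativity in baseline-negative men, who form a share *u* of the arm. Ignore missing-as-failure. Cure in the stratum is [0.85(0.92 - *u*) + 0.98*u*]/0.92: 85.4% at *u* = 3% and 85.8% at *u* = 6%, instead of 85.0%.

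**3. The missing interval, azithromycin arm**

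Taking 5, 10 and 15% of 123 gives 6, 12 and 18 LGV cases. The Newcombe interval is the method the SAP already uses. With *d* = *p*₁ - *p*₂ and Wilson limits (*l*ᵢ, *u*ᵢ):

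lower = *d* - √[(*p*₁ - *l*₁)² + (*u*₂ - *p*₂)²]; upper = *d* + √[(*u*₁ - *p*₁)² + (*p*₂ - *l*₂)²].

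| LGV+ cured | LGV- cured | Difference (points) | 95% CI |
|---|---|---|---|
| 4/6 | 102/117 | -20.5 | -57.5 to 4.2 |
| 8/12 | 97/111 | -20.7 | -48.8 to 0.2 |
| 12/18 | 91/105 | -20.0 | -43.5 to -1.2 |
| 13/18 | 91/105 | -14.4 | -38.1 to 2.7 |

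For the first row, the Wilson limits are 30.0 to 90.3% (4/6) and 79.9 to 92.1% (102/117). The first three differences are nearly equal, but their intervals are not. In the last row, one more cure brings zero back inside the interval.

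**4. How often the interval would exclude zero**

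Summing over both binomial distributions, with true cure 2/3 versus 87%, the interval excludes zero in 33%, 46% and 58% of trials with 6, 12 and 18 LGV cases. Its mean width is 59, 48 and 41 points.

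**The case against.** - **The analysis is the prespecified one.** Protocol 10.4.4.2 calls LGV subgroup a binary classification and plans treatment differences within it, and the tables match the stated outcome measure. This is correct, so nothing planned has been dropped. But the objective in both documents still names the effect of LGV, and no planned contrast estimates it.
- **A reader can compute the interval.** Each stratum has an All Subjects row with counts and a Wilson interval, as does each arm. This is also true. What is missing is the interval for the contrast, and a named objective should not leave that to the reader.
- **The effect of the classification rule may not show in print.** SAP 13 gives proportions to two decimals. With at most 5% untyped, 86.59% prints as 0.87 and 10.41 points as 0.10. The 1.6-point extreme needs 40% azithromycin cure in LGV. With the two thirds used in step 3, the same extreme cell gives 0.87(1 - 0.0341) + 0.667 × 0.0341 = 86.3%, a fall of 0.7 points. This stands: the case for the change is transparent labelling and does not depend on a large bias.
- **Negative is a fair label for a man with no CT detected.** It is arguable, and it affects only ITT, since CC and PP require a positive baseline NAAT. But he had no strain to type, so grouping him with typed non-LGV infections is not informative.
- **LGV status is not randomized, and subgroups are not powered (SAP 6.4).** Both are true. The added contrast should be descriptive, labelled observational, and untested.

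**Conclusion.** Both points hold, and both are minor. Read literally, SAP 3.3.7 puts indeterminate and not-done results in the LGV-negative stratum, and SAP 6.5 does not correct this. The numerical effect is probably small: at most 0.4 points on azithromycin cure if no more than 5% are untyped, and up to 1.6 points at 15% LGV, 20% untyped and 40% LGV cure. The first secondary objective would be reported with stratum proportions but no interval for the effect it names; on the assumed counts that interval is about 40 to 60 points wide. Adding it states the uncertainty and is unlikely to produce a positive finding. All sizes depend on LGV inputs that the documents do not supply. The primary comparison does not use LGV status.

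**What to change.** 1. In SAP 3.3.7 define three categories: positive (LGV detected); negative (PCR done on a CT-positive baseline swab, non-LGV result); undetermined (indeterminate or not done, including a CT-negative baseline swab).
2. In Tables 19-24 show undetermined as its own row block, with counts and cures by arm, so that the ITT tables still account for all randomized men.
3. In SAP 8.2.2 add a descriptive LGV-positive minus LGV-negative cure difference at Days 15 and 29, within each arm, with a Newcombe 95% CI and no test. The code in SAP 6.1.1, "Table treatment*analysisvariable / riskdiff(cl=Wilson", serves with LGV status in place of treatment, run by arm.
4. If a combined figure is wanted, use a Mantel-Haenszel risk difference stratified by arm with a Sato 95% CI. Show it beside the per-arm results, because it averages over any difference between arms. As an example, 12/18 versus 91/105 (azithromycin) with 17/18 versus 102/105 (doxycycline) gives -11.3 points (-24.5 to 1.8).
5. Record the changes in SAP 15, which now mentions only the per-protocol criteria, since the protocol describes a binary classification.

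The cost is SAP wording, one derived category, one row block in six tables and one short new table, because the Table 19 shell has no column for an LGV difference. The optional combined figure needs one new procedure. No new data are needed. The downsides are a slightly smaller LGV-negative stratum and wide intervals that will often include zero if LGV cases are few.
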